13 STATISTICAL CONSIDERATIONS

13.1 Objectives and Endpoints

13.1.1 Primary Safety Objective

The primary safety objective of the study is to evaluate the safety of the Omnipod Horizon™ System in preschool patients with type 1 diabetes.

13.1.1.1 Primary Safety Endpoints

The primary safety objective will be evaluated by summarizing the following events during Phase 2, and separately during Phase 3:

- Incidence rate of severe hypoglycemia (events per person months)
- Incidence rate of diabetic ketoacidosis (DKA) (events per person months)

13.1.2 Primary Effectiveness Objective

The primary effectiveness objective of this study is to evaluate the effectiveness of the Omnipod Horizon™ System

13.1.2.1 Primary Effectiveness Endpoints

There are two primary effectiveness endpoints.

- A1C at the end of Phase 2 compared to baseline A1C
- A1C at Visit 16, 19, 21, and 23 compared to baseline
- Percentage of time in range (70-180 mg/dL) during Phase 2, and separately during Phase 3 of the hybrid closed-loop phase compared to Phase 1 (standard therapy)

A1C-Phase 2

The end of Phase 2 (~13 weeks) A1C will be compared to baseline A1C as measured by the core laboratory by calculating the change from baseline in A1C at Visit 13 (~13 weeks) for each subject. The change in A1C is calculated as A1C at Visit 13 minus baseline A1C (where negative change indicates decrease or improvement in A1C). The null hypothesis associated with this endpoint states that the mean change in A1C is greater than or equal to zero. Rejection of the null hypothesis indicates that the observed data support the alternative hypothesis that the mean change in A1C is less than zero.

The hypotheses associated with the first primary endpoint are defined as:

$H_0: \mu \geq 0$

$H_1: \mu < 0$

where μ is the mean of the per subject differences in A1C from baseline to Visit 13.

A1C – Phase 3

A1C at Visit 16 (~6 months total HCL participation) will be compared to baseline A1C as measured by the core laboratory by calculating the change from baseline in A1C at follow-up visit for each subject.

The change in A1C is calculated as A1C at follow-up minus baseline A1C. There are no hypotheses associated with this endpoint.

Percentage of Time in Range 70-180 mg/dL -Phase 2

The percentage of time in range 70-180 mg/dL during Phase 2 of the hybrid closed-loop phase will be compared to Phase 1 (standard therapy) by calculating the change between the time in range percentages between Phase 2 of hybrid closed-loop and Phase 1 (standard therapy) for each subject. The change in percentage of time in range 70-180 mg/dL is calculated as the percentage of time in range during Phase 2 minus the percentage of time in range during Phase 1 (where positive change indicates increased time in range). The null hypothesis

associated with this endpoint states that the mean change in percentage of time in range 70-180 mg/dL is less than or equal to zero. Rejection of the null hypothesis indicates that the observed data support the alternative hypothesis that the mean change in percentage of time in range 70-180 mg/dL is greater than zero.

The hypotheses associated with this primary endpoint are defined as:

$H_0: \mu \leq 0$

$H_1: \mu > 0$

where μ is the mean of the per subject differences in percentage of time in range 70-180 mg/dL during Phase 2 compared to Phase 1.

Percentage of Time in Range 70-180 mg/dL – Phase 3

The percentage of time in range 70-180 mg/dL during Phase 3 of the hybrid closed-loop phase will be compared to standard therapy by calculating the change between the time in range percentages between Phase 3 of hybrid closed-loop and Phase 1 (standard therapy) for each subject. The change in percentage of time in range 70-180 mg/dL is calculated as the percentage of time in range during Phase 3 minus the percentage of time in range during Phase 1. There are no hypotheses associated with this endpoint.

13.1.3 Secondary Objective

The secondary objective of the study is to evaluate additional glycemic measures of effectiveness of the Omnipod Horizon™ System.

13.1.4 Secondary Endpoints

The secondary objective will be evaluated using the following per subject endpoints *with* prespecified hypotheses:

Glucose metrics from system CGM during the hybrid closed-loop phase for Phase 2 will be compared to Phase 1 overall:

- % of time > 180 mg/dL
- % of time < 70 mg/dL

Additional per subject secondary endpoints *without* prespecified hypotheses used to evaluate the secondary objective include:

- A1C:
 - A1C at the end of Phase 2 (Visit 13), at 6 months (Visit 16), and at the end of Phase 3 (Visit 23; approximately 15 months)
 - Change from baseline in A1C at the end of Phase 2 (Visit 13), at 6 months (Visit 16), and at the end of Phase 3 (Visit 23; approximately 15 months)
 - Proportion of subjects demonstrating an improvement from baseline in A1C at the end of Phase 2 (Visit 13), at 6 months (Visit 16), and at the end of Phase 3 (visit 23; approximately 15 months)

- Glucose metrics from system CGM during the hybrid closed-loop phase during Phase 2, and separately during Phase 3 will be compared to Phase 1 during the day, overnight, and overall:
 - Mean glucose
 - % of time in range 70-180 mg/dL
 - % of time in range 70-140 mg/dL
 - % of time > 180 mg/dL
 - % of time \geq 250 mg/dL
 - % of time \geq 300 mg/dL
 - % of time < 70 mg/dL
 - % of time < 54 mg/dL
 - Standard deviation
 - Coefficient of variation
- Percentage of time in hybrid closed-loop as proportion of overall device usage time during Phase 2, and separately during Phase 3
- Glucose management indicator (GMI) based on overall mean glucose during Phase 2, and separately during Phase 3 will be compared to Phase 1
- Insulin requirements during Phase 2, and separately during Phase 3 will be compared to Phase 1 during the day, overnight, and overall:
 - Total daily insulin (TDI) (units, units/kg)
 - Total daily basal insulin (units, units/kg)
 - Total daily bolus insulin (units, units/kg)
- Change from baseline in BMI (kg/m²) at end of Phase 2, and at end of Phase 3

Percentage of Time in Range >180 mg/dL

The percentage of time in range >180 mg/dL during Phase 2 will be compared to Phase 1 by calculating the change between the time in range percentages between Phase 2 and Phase 1 for each subject. The change in percentage of time in range >180 mg/dL is calculated as the percentage of time in range during Phase 2 minus the percentage of time in range during Phase 1. The null hypothesis associated with this endpoint states that the mean change in percentage of time in range >180 mg/dL is greater than or equal to zero. Rejection of the null hypothesis indicates that the observed data support the alternative hypothesis that the mean change in percentage of time in range >180 mg/dL is less than zero.

The hypotheses associated with this secondary effectiveness endpoint are defined as:

$$H_0: \mu \geq 0$$

$$H_1: \mu < 0$$

where μ is the mean of the per subject differences in percentage of time in range >180 mg/dL during Phase 2 compared to Phase 1.

Percentage of Time in Range <70 mg/dL

The percentage of time in range <70 mg/dL during Phase 2 will be compared to Phase 1 by calculating the change between the time in range percentages between the Phase 2 and Phase 1 for each subject. The change in percentage of time in range <70 mg/dL is calculated as the percentage of time in range during Phase 2 minus the percentage of time in range during Phase 1. The null hypothesis associated with this endpoint states that the mean change in percentage of time in range <70 mg/dL is greater than or equal to zero. Rejection of the null hypothesis indicates that the observed data support the alternative hypothesis that the mean change in percentage of time in range <70 mg/dL is less than zero.

The hypotheses associated with this secondary effectiveness endpoint are defined as:

$$H_0: \mu \geq 0$$

$$H_1: \mu < 0$$

where μ is the mean of the per subject differences in percentage of time in range <70 mg/dL during Phase 2 compared to Phase 1.

13.2 Sample Size

This is a single-arm, multi-center, prospective study. The sample size and study duration were determined to allow for adequate safety profile of the investigational device. The study will be claimed successful if rates of Severe Hypoglycemia and DKA during Phase 2 are considered acceptable compared to published rates.

In addition, a statistically powered sample size was determined for the two Phase 2 primary effectiveness endpoints. Since each of the Phase 2 primary effectiveness endpoints will be evaluated separately, the significance level will be adjusted so that the overall type I error can be maintained at one-sided 2.5% and each endpoint will be tested at one-sided 1.25%.

13.2.1 Primary Endpoint of A1C at End of Phase 2 (~13 Weeks) Compared to Baseline

The sample size estimation is based on the following assumptions:

- Mean difference between paired observations of A1C at the end of Phase 2 compared to baseline -0.5%
- Standard deviation of the difference between paired observations of A1C at the end of Phase 2 compared to baseline is 0.8%
- Power of 90% and one-sided significance level of 1.25%

The estimates for the mean difference and standard deviation of the difference between the paired observations were obtained from previous Omnipod studies, where subjects experienced a mean change in A1C of 0.38% over 3 months (standard pump therapy only), from 8.1 to 7.7%, n=85 (*data on file*). Based on the above assumptions, 35 subjects are required to provide evaluable data.

13.2.2 Primary Endpoint of Percentage of Time in Range 70-180 mg/dL During Phase 2 Compared to Phase 1

The sample size estimation is based on the following assumptions:

- Mean difference between paired observations of percentage of time in range 70-180 mg/dL during Phase 2 of hybrid closed-loop phase compared Phase 1 is 10%
- Standard deviation of the difference between paired observations of percentage of time in range 70-180 mg/dL during Phase 2 of hybrid closed-loop phase compared to Phase 1 is 10%%
- Power of 90% and one-sided significance level of 1.25%

The estimates for the mean difference and standard deviation of the difference between the paired observations were obtained from recent Omnipod study, G170143, where twelve (12) subjects aged 3.4-5.9 years experienced a mean change in percentage of time in range 70-180 mg/dL of $13.2 \pm 10.2\%$. Based on the above assumptions, 11 subjects are required to provide evaluable data.

To gather adequate safety and effectiveness data on the performance of the Omnipod Horizon™ System, a total of up to 80 subjects will be enrolled in the study in order to obtain a minimum of 60 evaluable subjects.

Subjects will be enrolled across 6-12 clinical study sites. No single site should enroll more than 24 subjects.

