13.4 Analysis of Primary and Secondary Endpoints

Both Phase 2 primary effectiveness endpoints will be tested independently of each other for statistical significance using a paired t-test at a one-sided significance level of 1.25%.

If at least one of the Phase 2 primary effectiveness endpoints are found to be significant, the testing for Phase 2 secondary endpoints can commence. The details on how the family-wise error rate will be maintained at the 2.5% significance level (one-sided) will be provided in the Statistical Analysis Plan (SAP). In addition, the Phase 2 primary effectiveness endpoints may also be tested for significance within a smaller cohort of subjects. The details of subgroup analyses and testing will also be detailed in the SAP.

There are no hypotheses associated with the other Phase 2 secondary endpoints or any of the Phase 3 endpoints. Summary statistics will be presented by age cohort for all endpoints, stratified by time points of interest (e.g., day vs. night, overall). The Phase 2 primary and secondary endpoints will be summarized for modified Intention to Treat (mITT) and Per Protocol (PP) analysis sets. If the PP analysis set does not differ from the mITT analysis set, separate analyses will not be presented. The data may be stratified by phase of the study, where the data collected in the standard therapy phase of the study will be compared to the data collected in the hybrid closed-loop phase of the study.

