4.1 SAMPLE SIZE

This is a single-arm, multi-center, prospective study. The sample size and study duration were determined to allow for an adequate safety profile of the investigational device. The study will be claimed successful if the incidence rates of severe hypoglycemia and diabetic ketoacidosis are considered acceptable compared to published rates.

In addition, a statistically powered sample size was determined for the two primary effectiveness endpoints. Since each of the primary effectiveness endpoints will be evaluated separately, the significance level will be adjusted so that the overall type I error can be maintained at one-sided 2.5%, and each endpoint will be tested at one-sided 1.25%.

A1C

The sample size estimation is based on the following assumptions:

- Mean difference between paired observations of A1C at the end of Phase 2 compared to baseline is -0.5%
- Standard deviation of the difference between paired observations of A1C at the end of Phase 2 participation compared to baseline is 0.8%
- Power of 90% and one-sided significance level of 1.25%

The estimates for the mean difference and standard deviation of the difference between the paired observations were obtained from previous Omnipod studies, where subjects experienced a mean change in A1C of 0.38% over 3 months (standard pump therapy only), from 8.1 to 7.7%, n=85 (data on file). Based on the above assumptions, 35 subjects are required to provide evaluable data.

Percentage of Time in Range 70-180 mg/dL

The sample size estimation is based on the following assumptions:

 Mean difference between paired observations of percentage of time in range 70-180 mg/dL during Phase 2 of hybrid closed-loop compared to Phase 1 is 10%

- Standard deviation of the difference between paired observations of percentage of time in range 70-180 mg/dL during Phase 2 of hybrid closed-loop compared to Phase 1 is 10%
- Power of 90% and one-sided significance level of 1.25%

The estimates for the mean difference and standard deviation of the difference between the paired observations were obtained from recent Omnipod Horizon study, G170143, where twelve (12) subjects aged 3.4-5.9 years experienced a mean change in percentage of time in range 70-180 mg/dL of 13.2 \pm 10.2%. Based on the above assumptions, 11 subjects are required to provide evaluable data.

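### The 11 subjects stated for time in range do not follow from the listed assumptions: 11 gives 74% power, and 90% needs 16

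*Protocol*

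**What the plan says.** Protocol 13.2.2 sets out the time-in-range (70-180 mg/dL) calculation. The mean paired difference "during Phase 2 of hybrid closed-loop phase compared Phase 1 is 10" percent, and the standard deviation of that difference "during Phase 2 of hybrid closed-loop phase compared to Phase 1 is 10" percent. The error and power line, which SAP 4.1 repeats, reads "Power of 90% and one-sided significance level of 1.25" percent. The conclusion, worded identically in both documents, is "Based on the above assumptions, 11 subjects are required to provide evaluable data".

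Both documents attribute the estimates to a feasibility study in which 12 children aged 3.4-5.9 years had a mean change of 13.2 with an SD of 10.2.

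The 1.25% comes from splitting an overall one-sided 2.5% between the two primary effectiveness endpoints: "each endpoint will be tested at one-sided 1.25" percent. Protocol 13.4 names the test, "using a paired t-test at a one-sided significance level of 1.25" percent, and SAP 4.2 says the same. For A1C, with a mean change of -0.5, an SD of 0.8 and the same power and level, the stated result is "Based on the above assumptions, 35 subjects are required to provide evaluable data".

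**The concern.** The documents tie 11 explicitly to the four inputs listed just above it. A standardized effect of 1.0 at one-sided 1.25% and 90% power looks too demanding for 11 subjects under a t-test with 10 degrees of freedom. If so, the stated number and the stated assumptions cannot both be right.

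The figure is one of only two power calculations for the primary effectiveness endpoints, and the sponsor intends to submit Phase 2 results for marketing clearance. A regulatory statistician who repeats the calculation will not obtain 11. The rule that the SAP prevails over the protocol does not help, because the SAP carries the same number. If 11 was really computed from the feasibility values, the text also makes the calculation look more cautious than it was: it lists an effect of 1.0 while the number rests on about 1.29.

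**Working it through.** **Inputs** (Protocol 13.2.2 and SAP 4.1): mean difference δ = 10, SD σ = 10, so δ/σ = 1.0; one-sided α = 0.0125; power 0.90. Test: paired t (Protocol 13.4, SAP 4.2). The count is of evaluable subjects, so no dropout allowance applies.

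**Formula.** Power(n) = P(T > t₁₋α,ₙ₋₁), where T has a noncentral t distribution with n − 1 degrees of freedom and noncentrality (δ/σ)√n. The required n is the smallest with power of at least 0.90. The normal approximation is n = ((z₁₋α + z₁₋β)/(δ/σ))².

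**Step 1: identify the method from A1C.** Here δ/σ = 0.5/0.8 = 0.625. The t-test power is 89.7% at n = 34 and 90.6% at n = 35, so n = 35, exactly as stated. The plain normal approximation gives 31.77, so 32, which does not match. Adding the usual small-sample term z₁₋α²/2 also gives 35.

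**Step 2: apply the same method to time in range, δ/σ = 1.0.**

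| n | Power, paired t-test | Power, normal approximation |
|---|---|---|
| 11 | 74.2% | 85.9% |
| 12 | 79.3% | 88.9% |
| 13 | 83.5% | 91.4% |
| 14 | 87.0% | 93.3% |
| 15 | 89.8% | 94.9% |
| 16 | 92.1% | 96.1% |

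The t-test needs 16. A simulation of 400,000 trials gave 74.4% at n = 11 and 92.2% at n = 16, in agreement.

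**Step 3: try the other methods on the same inputs.** Normal approximation: (2.241 + 1.282)² = 12.41, so 13. With the small-sample term: 15. Neither gives 11.

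**Step 4: look for where 11 could come from.**

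- Paired t-test, α = 0.0125, 90% power, feasibility values 13.2/10.2 = 1.294: power 89.5% at n = 10 and 93.1% at n = 11, so 11.
- Normal approximation with 10 and 10 at one-sided 2.5%: 10.51, so 11.
- Paired t-test with 10 and 10 at one-sided 5%: power 89.75% at n = 10 and 92.45% at n = 11, so 11.

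Each route changes at least one listed input. The first keeps the method, level and power that reproduce A1C and uses numbers printed in the same paragraph, which makes it the likeliest. The documents do not settle it.

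**Step 5: consequence at the planned size.** With 10 and 10 at α = 0.0125, t-test power is 99.97% at n = 35 and above 99.9% at n = 60.

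**The case against.** The strongest counter-argument concerns consequence, not arithmetic. Both documents say that sample size and duration were chosen mainly to give an adequate safety profile, with the power calculations as an addition. The target is at least 60 evaluable subjects from up to 80 enrolled, and within effectiveness A1C's 35 is the larger requirement. Study success is defined by the rates of severe hypoglycemia and DKA, and SAP 4.2 says the primary effectiveness endpoints will not support labeling claims. No planned analysis uses 11 subjects, and the t-test holds its 1.25% level at any sample size, so a significant result would not be undermined by this figure.

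All of that stands, and it limits how much the error matters. It does not make the sentence true: the plan says a number follows from four stated inputs, and it does not.

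A second objection is that the 13.2/10.2 explanation is only inferred, and that adopting it would replace the more cautious 10 and 10 with raw estimates from 12 subjects. That also stands. It means the alternative correction is open only if the sponsor confirms those values as the source.

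**Conclusion.** The stated figure is wrong as written in both documents. Under the listed assumptions and the planned paired t-test, 11 subjects give 74.2% power, about 16 percentage points below the stated 90%. The required number is 16, so 11 is 5/16, or 31%, too low.

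The conclusion rests only on inputs printed in the documents and on the named test. It survives a switch to the normal approximation (13) and to its small-sample correction (15). The single point that is inferred is the origin of 11.

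The error should be corrected because it sits in a primary-endpoint justification intended for regulatory use. It calls for no extra enrolment and no change to the analysis: with at least 60 evaluable subjects the endpoint has more than 99.9% power under the stated assumptions.

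**What to change.** In Protocol 13.2.2 and SAP 4.1, replace 11 with 16. This follows directly from the documents and keeps the more cautious assumptions of 10 and 10.

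If the sponsor's records show that 11 was computed from the feasibility values, the alternative is to keep 11 and list a mean of 13.2 and an SD of 10.2 as the assumptions in both documents. The text should not present 11 as the result of 10 and 10.

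The first option costs one number in each document; the second costs two input values in each. The A1C requirement of 35, the target of 60 evaluable from up to 80 enrolled, the 1.25% level and the planned test are all unchanged.

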13.3 Analysis Sets

The following analysis sets are planned for the study and will apply to the endpoints through the end of Phase 2. There are no prespecified analysis sets for Phase 3; all available data will be used to summarize Phase 3 endpoints.

13.3.1 ITT (Intention to Treat) Analysis Set

The ITT analysis set includes all subjects that are enrolled in the study. All safety analyses (other than primary analysis of primary safety endpoints) will be based on the ITT analysis set.

13.3.2 mITT (modified Intention to Treat) Analysis Set

The modified Intention to Treat (mITT) analysis set is a subset of the ITT analysis set. The mITT analysis set will consist of subjects who have entered the hybrid closed-loop phase of the study successfully. The mITT analysis set will be used as the primary analysis for the primary and secondary endpoints and other clinical outcome data.

13.3.3 PP (Per-Protocol) Analysis Set

The Per-Protocol (PP) analysis set is a subset of the mITT analysis set. Subjects will be included in the PP analysis set if they have a minimum of 80% system use during the hybrid closed-loop phase inclusive of Manual and hybrid closed-loop (Automated) modes over a minimum duration of 10 weeks and have completed the study without major protocol deviations. The PP analysis set will be used as supportive analysis for the endpoints. The following will be considered major protocol deviations:

- Major inclusion/exclusion criterion deviation
- Significant protocol non-compliance that may confound the study objective data (e.g., use of prohibited medications)

The list of subjects excluded from the PP analysis set will be determined prior to analysis. If the PP analysis set does not differ from the mITT analysis set, separate analyses will not be presented.

13.4 Analysis of Primary and Secondary Endpoints

Both Phase 2 primary effectiveness endpoints will be tested independently of each other for statistical significance using a paired t-test at a one-sided significance level of 1.25%.

If at least one of the Phase 2 primary effectiveness endpoints are found to be significant, the testing for Phase 2 secondary endpoints can commence. The details on how the family-wise error rate will be maintained at the 2.5% significance level (one-sided) will be provided in the Statistical Analysis Plan (SAP). In addition, the Phase 2 primary effectiveness endpoints may also be tested for significance within a smaller cohort of subjects. The details of subgroup analyses and testing will also be detailed in the SAP.

There are no hypotheses associated with the other Phase 2 secondary endpoints or any of the Phase 3 endpoints. Summary statistics will be presented by age cohort for all endpoints, stratified by time points of interest (e.g., day vs. night, overall). The Phase 2 primary and secondary endpoints will be summarized for modified Intention to Treat (mITT) and Per Protocol (PP) analysis sets. If the PP analysis set does not differ from the mITT analysis set, separate analyses will not be presented. The data may be stratified by phase of the study, where the data collected in the standard therapy phase of the study will be compared to the data collected in the hybrid closed-loop phase of the study.

